11.8 Minimization of Loss to Follow-up

Subject follow-up is extremely important for the conduct of a clinical study. The expectation is to maintain the highest rate of follow-up compliance possible throughout this study. Subjects that are study completed as lost to follow-up will not be replaced. In an effort to minimize the number of subjects lost to follow-up, the following recommendations and/or study requirements are essential to ensure proper patient selection and compliance:

- Patient Eligibility: Subjects will be selected according to the inclusion/exclusion criteria detailed in Section 8 and are expected to return for all follow-up visits.
- Patients Counseled: Patients will be counseled during the Informed Consent process on the importance of returning for follow-up visits.
- Patient Exclusion: Patients who are not willing to return for study required follow-up visits and/or are not willing to comply with the follow-up schedule will not be considered for enrollment into the study.
- Subject Due Listings: In addition to proper patient selection, Zimmer Biomet will provide subject due notices to the sites on a regular basis in order to track each study participant and monitor adherence to the required follow-up visit timeframes. The subject due listings will facilitate scheduling the subjects for their return office visits.
- Contact Tracking: Attempts to contact subjects will be documented in the study subject's medical record. It is recommended that the first three attempts be made by telephone. If after three calls, contact has not been successful, the below is suggested prior to terminating the study subject from the study:

If	Then
a response is not received following attempts to reach the subject by phone	the Investigator could send a letter to the patient explaining the follow-up agreement per informed consent.
a response is not received from the Investigator's letter	the Investigator could use any additional contacts provided by the subject to contact the subject.
The subject missed three consecutive visits and all attempts to contact the subject are unsuccessful, or the subject is contacted and chooses to withdraw from the study	the Study Completion form may be completed and will specify the reason the patient is no longer participating in this study.

11.9 Surgical Reoperation or Revision

A reoperation of the index hip or revision of the SCP injection site may be performed at the discretion of the Investigator (e.g., due to progressive pain or disability, etc.). A reoperation is defined as any surgical procedure on the index hip. For the purposes of this protocol, a revision will be defined as any partial or total joint arthroplasty or any fusion, bone fixation, bone grafting, or bone substitute procedure in the study hip.

If the reoperation occurs due to an adverse event, the event should be documented on a Serious Adverse Event Form and an Exit Form completed, and the subject exited from the study.

In the event that a revision occurs (defined as any partial or total joint arthroplasty or any fusion, bone fixation, bone grafting, or bone substitute procedure in the index hip), the subject will be exited from the study. A Serious Adverse Event Form and an Exit Form will be completed.

Use of any postoperative injections into the index hip should be recorded on the Medication Form at the next questionnaire completion window.

12 Reporting

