10.4 Study Design

This study is designed as a post-market, single arm, non-randomized multi-center investigation.

Male and female subjects, at least 18 years of age, with at least one subchondral bone defect in the form of a cyst and/or bone marrow lesion (BML), insufficiency fracture or bone defect associated with early stage avascular osteonecrosis (AVN) in the femoral head, femoral neck and/or acetabulum who are suitable candidates for use of AccuFill during the Subchondroplasty Procedure are eligible for enrollment in this study.

A maximum of 15 study sites, in the United States of America, will enroll a target of 50 subjects.

Each Investigator must obtain IRB approval, or favorable opinion by an EC, prior to consent of the first subject; no study-related procedures can occur without the approval and oversight of a registered IRB or EC. If the study site does not have an IRB of record, a central IRB may be utilized upon approval by Zimmer Biomet.

Demographics, medical history, hip history and use of pain medication and therapy will be recorded at the time of subject consent. Additionally, patient reported outcomes measures will be obtained pre-operatively. Operative details including the SCP Procedure, concomitant surgical procedures and intraoperative safety events will be recorded at the time of surgery. Prospective subjects will be considered enrolled in this study once their Subchondroplasty Procedure has been performed.

Subjects will complete only the Numeric Pain Scale at 2 weeks post-operatively. Thereafter, subjects will complete self-reported outcomes measures post-operatively at 6 weeks, 12 weeks, 6 months, 1 year and 2 years. These measures include information on pain medication and therapy, pain levels, function, activity and subject satisfaction. Screening for adverse events and conversion will occur throughout the study.

Subjects will complete the study at 2 years or will be withdrawn if they undergo conversion of the Subchondroplasty site. For the purposes of this protocol, a conversion will be defined as

total hip arthroplasty or any procedure involving removal of the AccuFill material on the index hip.

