11.7 Follow-up Procedures

In order to minimize the burden to patient and physician, patients will be enrolled at the physician's office, but will not be required to come back to the office for follow-up visits.

A Numeric Pain Score will be collected at the first post-operative standard of care visit at approximately 7-21 days.

Thereafter, subjects complete self-reported outcomes measures post-operatively at 6 weeks, 12 weeks, 6 months, 1 year and 2 years. These measures include:

- Use of pain medication and therapy
- Subject-reported outcomes:
 - Numeric Pain Scale
 - Modified Harris Hip Score
 - Hip Outcome Score
 - EQ-5D
 - Subject Global Satisfaction Survey

The post-operative visit data must be collected for each enrolled subject via email, in-person, regular mail or telephone (with an IRB approved phone script). If the subject is not seen in person, a member of the study staff will contact the subject by telephone at the aforementioned time points to inquire about their outcomes, any conversion surgeries, and adverse events.

Follow-up evaluations are detailed in Table 1— Schedule of Events. Follow-up is to occur within the windows described in Table 1.

The study database will be configured to send an email notification to subjects at the beginning of each specified visit window with a reminder that they need to complete the surveys. This email will contain a method to allow the subjects to complete their surveys electronically via the database's electronic Patient Reported Outcomes (ePRO) system.

Prior to contacting the study subject to assess potential adverse events by telephone, a member of the study staff will check to confirm whether these surveys have been completed electronically or not. If the subject has not completed the evaluation yet, a member of the study staff will ask if the subject would like to complete the questionnaires by phone, email or if they would like a copy of the surveys to be mailed out to them. Mailed surveys will be sent with a stamped, return envelope. The subject should be instructed to return the surveys within one week and to include the date of completion at the top of any of the pages. Any subject survey forms that are not collected via the database's ePRO system are to be maintained in the subjects' study files as source documents.

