12.4.4 Subject Withdrawal

Study participation may be discontinued through surgical conversion (Total Hip Arthroplasty or total removal of AccuFill), withdrawal of consent, Investigator decision or death. A subject may voluntarily withdraw their consent from the study at any time without prejudice or affecting their future medical treatment. Investigators may withdraw a subject due to non-compliance with the protocol or follow-up questionnaire schedule, or for reasons of medical discretion.

All consented subjects who are withdrawn/ discontinued from the study should have an End of Study form completed to explain why they are no longer participating in the study.

When a subject withdraws or is withdrawn, all study procedures completed and data collected prior to the date of withdrawal will be submitted to the sponsor and included in the study database, unless the subject requests otherwise in writing.

Should a subject who previously chose to withdraw wish to re-enter the study, a new Informed Consent will be required. The site may resume scheduled follow-up visits from the subject's last follow-up visit.

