12.4.8 Study Termination

Study subject participation is expected to end upon completion of the subject's two-year follow-up visit unless the subject voluntarily withdraws from the study, is withdrawn from the study by the Investigator, is lost to follow-up, undergoes revision to remove a study device, or expires. Reason(s) for study completion must be documented on the **Study Completion** case report form.

If the Sponsor decides to terminate the study early, the Sponsor will inform the Investigators of the reason for early study termination. It is the responsibility of the Investigators to inform their IRB or EC as applicable according to local and national laws/regulations.

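### Section 11.9 exits subjects after any adverse-event-driven reoperation of the index hip, even with AccuFill still in place, so scheduled safety screening stops for a small group selected by a harm

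*Combined protocol and SAP*

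**What the plan says.** Section 11.9 (Surgical Reoperation or Revision) gives a broad definition: "A reoperation is defined as any surgical procedure on the index hip". Where an adverse event is what led to the reoperation, the instruction reads: "the event should be documented on a Serious Adverse Event Form and an Exit Form completed, and the subject exited from the study". No condition refers to revision, conversion or removal of AccuFill. Revision is defined separately and has its own exit rule in the next paragraph.

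Section 10.4 (Study Design) states: "Subjects will complete the study at 2 years or will be withdrawn if they undergo conversion of the Subchondroplasty site". Conversion there means total hip replacement or surgery that takes AccuFill out of the index hip. The same section commits to follow-up for safety: "Screening for adverse events and conversion will occur throughout the study".

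Section 12.4.4 (Subject Withdrawal) says: "Study participation may be discontinued through surgical conversion (Total Hip Arthroplasty or total removal of AccuFill), withdrawal of consent, Investigator decision or death". It adds: "Investigators may withdraw a subject due to non-compliance with the protocol or follow-up questionnaire schedule, or for reasons of medical discretion". Section 12.4.8 (Study Termination) ends participation early when the subject withdraws voluntarily or "is withdrawn from the study by the Investigator, is lost to follow-up, undergoes revision to remove a study device, or expires".

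For subjects not seen in person, section 11.7 (Follow-up Procedures) has study staff "contact the subject by telephone at the aforementioned time points to inquire about their outcomes, any conversion surgeries, and adverse events". Section 10.7.1 bases the safety assessment on how often adverse events occur, and 12.4.9 limits what is reported to the sponsor to events possibly or definitely related to the device or procedure.

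**The concern.** The reoperation rule in 11.9 reaches a group that no other rule exits by name: subjects whose second operation was caused by an adverse event, was not a joint replacement, fusion, fixation, graft or bone-substitute procedure, and left AccuFill where it was. Evacuation of a hematoma or surgery for a re-opened wound would be examples; section 6.4.1 lists both underlying complications as risks.

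What ends observation here is a recorded harm. For a reoperation that is neither a revision nor due to an adverse event, 11.9 gives no exit instruction. Subjects who have already had a complication serious enough for surgery therefore leave scheduled screening while the implant remains. What can be missed afterwards is conversion and later events related to the device or the Subchondroplasty Procedure.

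Sites also lack one consistent list. One that works from 10.4 could keep such a subject to 2 years, while one that works from 11.9 would complete an Exit Form.

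**Working it through.** **1. Surgical exit reasons, side by side**

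| Section | Surgical reason | Wording | Names this group? |
|---|---|---|---|
| 10.4 | Conversion | will | No |
| 11.9, reoperation | Any index-hip surgery due to an adverse event | should | Yes |
| 11.9, revision (exit form also in 12.4.2) | Joint replacement, fusion, fixation, graft or bone substitute | will | No |
| 12.4.4 | Hip replacement or total removal of AccuFill | may | No; Investigator discretion only |
| 12.4.8 | Revision that removes a study device | listed | No; Investigator withdrawal only |

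Only the reoperation sentence in 11.9 covers the group by name.

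**2. What stops at exit**

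Section 12.4.4 keeps the data collected before withdrawal, and no section schedules contact afterwards. The triggering event itself goes on the Serious Adverse Event Form. Its outcome might be updated through a sponsor request (section 13) or a data query (12.2.5), but no follow-up of it is scheduled. Complications of the second operation might not be reportable even if the subject stayed, because 13.2.3 treats complications of concomitant treatment that the plan does not impose as unrelated.

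**3. Scheduled contact lost per exited subject**

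Table 1 has six follow-up time points: 2 weeks, 6 weeks, 12 weeks, 6 months, 1 year and 2 years. Months lost = 24 − time of exit, with 30.44 days per month (for example, 14/30.44 = 0.46, and 24 − 0.46 = 23.54).

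| Exit just after | Contacts lost of 6 | Months lost of 24 |
|---|---|---|
| 2 weeks | 5 | 23.54 (98.1%) |
| 6 weeks | 4 | 22.62 (94.3%) |
| 12 weeks | 3 | 21.24 (88.5%) |
| 6 months | 2 | 18 (75.0%) |
| 1 year | 1 | 12 (50.0%) |

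These are calendar losses. They do not say how many events would be missed.

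**4. Effect on counts and percentages**

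Let m of 50 subjects exit under this rule, c conversions occur among the other 50 − m, and x unseen conversions occur among the m. Full follow-up gives (c + x)/50. The report gives c/50 if everyone stays in the denominator, or c/(50 − m) if exited subjects are removed. Section 16.3 does not say which. The values of m, c and x below are assumptions for illustration; the documents give none.

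| m, c, x | Full follow-up | Reported, all 50 | Reported, exits removed |
|---|---|---|---|
| 5, 5, 1 | 6/50 = 12.0% | 5/50 = 10.0% | 5/45 = 11.1% |
| 5, 5, 0 | 5/50 = 10.0% | 5/50 = 10.0% | 5/45 = 11.1% |
| 1, 5, 0 | 5/50 = 10.0% | 5/50 = 10.0% | 5/49 = 10.2% |

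The count is low by x, so it can only be too low. With exits removed, the percentage is too low only if x/m > c/(50 − m). In row 1, 1/5 = 0.20 exceeds 5/45 = 0.11, so it is too low. In row 2, 0 is below 0.11, so it is too high.

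**5. Power, for context**

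The sample size in 16.1 reproduces: difference 31.4 − 18.0 = 13.4, SD 22.4, one-sample t-test, two-sided alpha 0.05 gives n = 24 with power 0.801, and 24/(1 − 0.25) = 32. With 50 enrolled and 25% attrition, 37 remain (power about 0.94). If a further 2% to 10% of the 50 were lost to this rule (assumed), 36 to 32 remain and power is about 0.94 to 0.91. Power is not the issue.

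**The case against.** **Section 10.4 does not say that conversion is the only exit.** A reader might infer a direct contradiction between 10.4 and 11.9. The documents do not support that. The sentence in 10.4 also leaves out death, withdrawal of consent and loss to follow-up, all of which end participation elsewhere. Section 11.9 can be read as adding a rule where 10.4 is silent. This objection stands, and the point is an inconsistency.

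**The exit is worded with *should*, and Investigators may withdraw subjects anyway.** The revision rule in 11.9 uses *will*, so the reoperation exit is weaker than mandatory. That also stands. Yet case-by-case discretion does not explain an instruction that applies to every such reoperation, and an advisory reading leaves sites with less common guidance.

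**The same loss follows a revision.** True: a revised subject may also still carry AccuFill. Whether revision should end follow-up is a separate question, not argued here.

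**The group is small, and conversion is not a listed endpoint.** Both are correct. Section 12.4.9 also asks sites to record the diagnosis behind a hip replacement, not the replacement itself. But 10.4 commits to screening for conversion, and the arithmetic above applies equally to subjects with a later related adverse event, which 10.7.1 does assess.

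**Exit keeps the scores free of a second operation.** This is a fair reason to identify or handle later Modified Harris Hip Scores separately. It is not a reason to stop asking about safety.

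**Conclusion.** The concern holds as an inconsistency with a bounded consequence. Following 11.9 as written ends scheduled screening for later conversion and related adverse events in a narrow group chosen because a harm occurred, while AccuFill remains in the hip. Each later event that goes unseen lowers the count by one; with 50 subjects, one subject is 2 percentage points.

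The total effect is unknown because the documents give no reoperation rate. A reader might infer that complication or conversion percentages will be understated. That does not follow: only the counts have a fixed direction, and the percentages depend on a denominator that 16.3 leaves open. Nor does the point suggest that the triggering event is lost or that power is materially reduced.

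The conclusion rests on two readings: that the definition of reoperation means what it says, and that exit ends the Table 1 contacts because no section provides any afterwards. It is a worthwhile, low-cost correction, not a serious flaw in the study.

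**What to change.** - In 11.9, limit surgical exit to revision or conversion.
- Use one list of surgical exit reasons in 10.4, 11.9, 12.4.4 and 12.4.8.
- Keep other reoperated subjects on the existing Table 1 contacts to 2 years, unless consent is withdrawn. At a minimum, collect related adverse events, conversion and the outcome of the triggering event.
- Record the reoperation and its date, so that scores after it can be identified. How those scores are analysed can be decided separately.

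The cost is a protocol amendment with IRB approval at up to 15 sites, and full CIRC review if it is classed as substantive; it can be bundled with another amendment. Each affected subject adds at most 5 contacts (exit just after 2 weeks), all already in the schedule and possible by telephone, email or mail, with no new visits or procedures. The safety summary may look slightly less favourable.

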10.7.1 Primary Endpoint

The primary endpoint is defined by the overall group mean improvement from baseline of the Modified Harris Hip Score at the two year time point. The safety of the system will be assessed by monitoring the frequency and incidence of adverse events. Relation of the events to implant (Accufill®), instrumentation (SCP® Surgical Instrumentation) and/or procedure should be specified.

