12.4.2 Revision

In the event that revision of the SCP surgical site in the index hip is necessary, the Investigator will determine the best treatment and/or revision method for the subject. Once the revision surgery has been completed, the Investigator or qualified Designee must complete a **Serious Adverse Event** form and a **Study Exit** form.

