12.4.9 Adverse Events

An adverse event (AE) is defined as an untoward medical occurrence, unintended disease or injury, or untoward clinical signs (or change or worsening of a pre-existing medical condition) in a patient, which may or may not have an association with the device or procedure. In addition an adverse device effect is defined as ‘any untoward and unintended response to a medical device’.

Each Adverse Event Form should only include one adverse event. When reporting an adverse event, it is important to record the diagnosis rather than the symptoms, event or treatment. For example, a subject who undergoes a Total Hip Arthroplasty after the Subchondroplasty Procedure may have had the procedure due to increased pain caused by hip osteoarthritis. In this case, ‘Severe Osteoarthritis’ or something similar (as determined by the Investigator) should be recorded as the diagnosis rather than ‘Total Hip Arthroplasty’. Abbreviations/colloquialisms should also be avoided when recording the diagnosis.

For this study, **only AEs which are possibly or definitely related to the device or procedure will be reported to the sponsor**. The determination whether the AE is related to the device or procedure will be based upon whether a causal relationship between the device or procedure and the AE is at least a reasonable possibility, i.e., the relationship cannot be ruled out. A causal relationship cannot be ruled out if, in the medical judgment of the Investigator, the effect follows a reasonable temporal association with the use of the device.

For this study, device implies the AccuFill Bone Substitute Material and procedure implies the Subchondroplasty Procedure.

13 Safety Management – Medical Events/Adverse Events

Adverse events are required to be reported on the **Adverse Event Report** case report form. The completed **Adverse Event Report** case report form must be submitted to the Sponsor in a timely manner. The Investigator or Designee will also promptly provide the Sponsor with any additional requested information required for the Sponsor to comply with regulatory requirements. If applicable per their reporting requirements, the Investigator or Designee will also report applicable adverse event(s) to their IRB or EC.

The following definitions are from ISO 14155:2020.

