13.1.2 Serious Adverse Event (SAE)

A Serious Adverse Event is an adverse event that led to any of the following:

- death,
- serious deterioration in the health of the subject, users or other persons as defined by one or more of the following:
 - a life-threatening illness or injury, or
 - a permanent impairment of a body structure or a body function including chronic diseases, or
 - in-patient or prolonged hospitalization, or
 - medical or surgical intervention to prevent life-threatening illness or injury or permanent impairment to a body structure or a body function, led to fetal distress, fetal death or a congenital abnormality or birth defect including physical or mental impairment.

Note: Planned hospitalization for a pre-existing condition, or a procedure required by the protocol, without serious deterioration in health, is not considered a serious adverse event.

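### An index-hip revision judged unrelated is reportable under Sections 11.9 and 12.4.2 but not under 12.4.9, so the adverse event counts depend on which rule a site follows

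*Combined protocol and SAP*

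**What the plan says.** All references are to the combined protocol and SAP.

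- **Section 11.9** defines the event broadly: "a revision will be defined as any partial or total joint arthroplasty or any fusion, bone fixation, bone grafting, or bone substitute procedure". When one occurs in the index hip, "A Serious Adverse Event Form and an Exit Form will be completed". For other reoperations the trigger is conditional: "If the reoperation occurs due to an adverse event, the event should be documented on a Serious Adverse Event Form".
- **Section 12.4.2** repeats the duty for revisions: "Once the revision surgery has been completed, the Investigator or qualified Designee must complete a" Serious Adverse Event form, together with an exit form.
- **Section 12.4.9** restricts what leaves the site: "only AEs which are possibly or definitely related to the device or procedure will be reported to the sponsor". Its worked example is a hip replacement after Subchondroplasty done for pain from osteoarthritis. There a diagnosis such as severe osteoarthritis "should be recorded as the diagnosis rather than" the operation.
- **Section 10.7.1**, under the primary endpoint heading, adds: "The safety of the system will be assessed by monitoring the frequency and incidence of adverse events". Section 16.3 summarises complications as counts and percentages.

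**The concern.** Sections 11.9 and 12.4.2 apply no relatedness test. Section 12.4.9 applies one to all adverse events and makes no exception for revisions. A site that rates a hip replacement as unrelated is told by two sections to complete a Serious Adverse Event form, and by a third that unrelated events do not go to the sponsor. No section gives an order of precedence.

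Revision or conversion is the main way this procedure can fail, and the safety result is a descriptive count. If sites resolve the conflict differently, the pooled percentage mixes two counting rules. Even when the event is reported, recording only the diagnosis means that the adverse event listing need not show that an operation took place.

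**Working it through.** **1. One event under each rule.** Take a total hip arthroplasty on the index hip, rated by the investigator as not related.

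| Section | Trigger | Relatedness test | Result |
|---|---|---|---|
| 11.9 | any index-hip revision, including arthroplasty | none | Serious Adverse Event form |
| 12.4.2 | revision of the treated site in the index hip | none | Serious Adverse Event form, mandatory |
| 12.4.9 | any adverse event | possibly or definitely related | not reported to the sponsor |

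Sections 11.9 and 12.4.2 agree with each other, so the conflict is between those two and 12.4.9.

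**2. Can the rules be read together?** One attempt is that the form is completed but stays at the site. That fits poorly with the opening of Section 13, which has completed adverse event forms submitted to the sponsor. Another is that the specific rule (11.9, 12.4.2) overrides the general one. But 12.4.9 is also written specifically for this study, and its own example is a hip replacement.

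**3. How it reaches the results.** Table 1 lists one Adverse Event form (CRF 11) and no separate serious event or revision form. Section 16.3 plans no separate revision or conversion summary. The adverse event record is therefore the stated source for the safety percentages. With 50 subjects over up to 15 sites (50 / 15 = 3.3 per site), a difference in reporting practice could not be told apart from a difference in event rate.

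**4. Scale, by assumption.** The documents state no hip revision rate, so there is no figure to reproduce. The only revision rate given is 30% at two years, from a knee study (Section 6.1). I use it as the top of an assumed range. Let r be the share revised and s the share of revisions judged related.

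- Count under 11.9 and 12.4.2: R = 50 × r
- Count under 12.4.9: R × s, rounded
- Intervals: exact (Clopper-Pearson) 95%

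| r | R, under 11.9 and 12.4.2 | under 12.4.9, s = 75% | under 12.4.9, s = 0 (extreme bound) |
|---|---|---|---|
| 10% | 5/50 = 10% (3.3 to 21.8) | 3.75, so 4/50 = 8% (2.2 to 19.2) | 0/50 (0 to 7.1) |
| 20% | 10/50 = 20% (10.0 to 33.7) | 7.5, so 8/50 = 16% (7.2 to 29.1) | 0/50 (0 to 7.1) |
| 30% | 15/50 = 30% (17.9 to 44.6) | 11.25, so 11/50 = 22% (11.5 to 36.0) | 0/50 (0 to 7.1) |

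If sites differ in practice, the pooled count lies between the columns. These rows describe chosen inputs and do not forecast the trial. The sample size in Section 16.1 is not affected.

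**The case against.** The best defence is that few revisions would be filtered out. Section 12.4.9 treats an event as related when a link cannot be ruled out and accepts reasonable timing as enough. Section 13.2.1 ties a rating of None to the absence of a temporal relationship, and Section 13.2.2 puts weak or unassessable cases in the possible category. This largely stands: s = 0 at every site would go against these definitions. It does not close the gap, because Section 13.2 also tells assessors to weigh the natural history of the disease, and the example in 12.4.9 attributes the operation to osteoarthritis.

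A second defence is that the operations are captured elsewhere. Section 10.4 screens for conversion throughout, Section 11.7 has staff ask about it by telephone when the subject is not seen, and Sections 12.4.4 and 12.4.8 require the reason for leaving to be documented. Section 13.3 has the sponsor review submitted events. This also stands in part: many revisions could be recovered. But no section feeds the exit forms into the safety tables, and sponsor review cannot reach an event that was not submitted.

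Third, the example in 12.4.9 only tells the site which term to write and does not forbid counting the event. That is correct. The loss is of the procedure from the record, which is a smaller matter than non-reporting.

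**Conclusion.** The inconsistency is real and should be corrected. For an index-hip revision rated unrelated, Sections 11.9 and 12.4.2 require a report and Section 12.4.9 does not. Its size cannot be fixed from the documents. It grows with the revision rate and with the share judged unrelated, neither of which is given, and the safeguards above reduce it.

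A reader might infer more than the text supports:

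- **A third, conflicting definition in Section 13.1.2.** Its note says "Planned hospitalization for a pre-existing condition, or a procedure required by the protocol, without serious deterioration in health, is not considered a serious adverse event". Applying this to a hip replacement is strained. Section 11.9 gives progressive pain or disability as grounds for revision, and 13.1.2 itself lists in-patient stay and certain surgical interventions as serious.
- **That serious event incidence is a primary endpoint.** Section 10.7.1 speaks of adverse events, not serious ones, and the outcome it defines is the mean change in Modified Harris Hip Score. Safety is descriptive, with no test or threshold.
- **That counts would differ several-fold, or that revision will be the commonest serious event.** No figure in the documents supports either statement.

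**What to change.** Reconcile the passages as follows.

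1. In Section 12.4.9, state that the related-only limit does not apply to index-hip revisions for which 11.9 and 12.4.2 already require the form.
2. On that form, record both the diagnosis and the procedure performed. Make clear whether CRF 11 serves as the Serious Adverse Event form.
3. In Section 16.3, add a safety line for index-hip revisions or conversions in all subjects, regardless of relatedness, and show serious adverse events with and without them. The line needs one stated list of procedures, because revision in 11.9 and conversion in 10.4 and 12.4.4 differ in scope.
4. Optionally, add a sentence to the note in Section 13.1.2 on how it applies to surgery on the index hip.

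The cost is protocol wording, one form field and one tabulation. The form itself is already mandated. The reported event percentage may look less favourable.
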